### 14.3. Efficacy Analysis

#### 14.3.1. General Considerations

This study will compare the activity of AVXS-101 administered IV versus the natural observational results from PNCR [21] in terms of functional independent sitting and survival rate. The ability to thrive and the ability remain independent of ventilatory support will also be assessed.

The analysis of the co-primary and co-secondary efficacy endpoints will be performed for the ITT and efficacy completers population. The analysis based on the ITT population will be considered as the primary analysis. In the case of missing data, observed data will be used for the analyses.

Unless otherwise specified, the baseline measurement is defined as the last non-missing measurement collected prior to or on the day of gene replacement therapy infusion (e.g., on or before Day 1 visit).

#### 14.3.2. Primary and Secondary Efficacy Analysis

Primary and secondary efficacy analyses will be based on the ITT population, those patients that are symptomatic with biallelic- deletion mutations of *SMN1* and 2 copies of *SMN2* without the *SMN2* gene modifier mutation (c.859G>C). These analyses are to test the superiority of AVXS-101 to the results from natural observation study (PNCR) [21].

The first co-primary efficacy hypothesis to be tested is:

$$\begin{aligned} \mathbf{H}_0: p_{AVXS-101} &= 0.1\% \\ &\textit{versus the alternative} \\ \mathbf{H}_a: p_{AVXS-101} &> 0.1\%, \end{aligned}$$

where  $p$  is the proportion of functional independent sitting for at least 30 seconds at the 18 months of age study visit.

The second co-primary efficacy hypothesis to be tested is:

$$\begin{aligned} \mathbf{H}_0: p_{AVXS-101} &= p_{HISTORICAL-FINKEL} \\ &\textit{versus the alternative} \\ \mathbf{H}_a: p_{AVXS-101} &\neq p_{HISTORICAL-FINKEL}, \end{aligned}$$

where  $p$  is the proportion surviving at 14 months of age.

Primary efficacy endpoints will be examined on the ITT population. Testing for the first co-primary endpoint, functional independent sitting will first be performed using 1-sided exact binomial test. Only if the null hypothesis of equality in proportion of functional independent sitting is rejected at  $p < 0.025$ , will the co-primary endpoint survival improvement be tested using 2-sided Fisher's Exact test on the ITT population, comparing to matched patients from natural observational study (PNCR). This hierarchy approach strongly protects the Type I error rate.

The hypothesis for both co-secondary efficacy endpoints to be tested is:

$$\begin{aligned} \mathbf{H}_0: p_{AVXS-101} &= 0.1\% \\ &\textit{versus the alternative} \\ \mathbf{H}_a: p_{AVXS-101} &> 0.1\%, \end{aligned}$$

where  $p$  is the proportion of patients maintaining the ability to thrive/are independent of ventilatory support.

One-sided exact binomial tests will be executed for secondary efficacy analyses on the ITT population.

A sensitivity analysis will be conducted by repeating the primary efficacy analysis on the efficacy completers analysis population.

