Assuming the true response rate for the primary endpoint is actually zero (or as low as 0.1%) in the population of interest of the historical control, the first co-primary efficacy endpoint hypothesis is whether the AVXS-101 treated patients achieve a response rate greater than 0.1%. Based upon preliminary results from the ongoing Phase 1 clinical study AVXS-101-CL-101, at least 40% of treated patients in the ITT population are expected to achieve the co-primary efficacy endpoint of functional independent sitting for at least 30 seconds at the 18 months of age visit. With the assumption for the true response rate of AVXS-101 for the primary endpoint being in the range of 30% - 40%, a sample size of 15 patients that meet ITT criteria will be enrolled and assuming approximately 30% of patients

are excluded from analysis, would yield an ITT population that would provide power of > 90% to detect a significant difference from 0.1% with  $\alpha = 0.025$  using a 1-sided exact test for a binomial proportion.

The second co-primary efficacy endpoint of survival at 14 months of age will be evaluated by comparing the results observed in the ITT population with the results from the age and gender-matched control patients selected from existing natural history data sets (PNCR) [*Neurol.* 2014; 83(9):810-817]. It is anticipated that 75% of patients in the PNCR population would not survive beyond 13.6 months of age, and that these control patients will represent a 25% survival rate based upon the natural history of the disease. Based upon preliminary results from the ongoing Phase 1 clinical study (AVXS-101-CL-101), at least 80% of patients in the ITT population are expected to survive, as defined, through 14 months of age. With this efficacy, an enrolled sample size of 15 patients that meet ITT criteria (assuming 30% of patients are excluded from the analysis) would yield an ITT population that would provide power of > 80% to detect a significant difference from the historical control with  $\alpha = 0.05$  using a 2-sided Fisher's Exact test.

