#### **12.1.7. Pulmonary Examinations**

Pulmonary examinations will be performed by a pulmonologist or appropriate individual as per standard institutional practice at each scheduled visit except Day 1 ([Appendix 5](#)). Prior to study entry, a pulmonologist or appropriate individual as per standard institutional practice will review and document ventilator usage in the 2 weeks prior to screening.

Patients may be fitted with non-invasive ventilatory support at the discretion of the pulmonologist or appropriate individual as per standard institutional practice and/or Investigator. Non-invasive ventilatory support equipment will be provided by AveXis through a third-party vendor. Should the patient require non-invasive ventilatory support at any time during the study, the equipment provided by AveXis must be used.

Patients requiring non-invasive ventilatory support will be asked to bring their machine(s) to each study visit such that the study staff can remove an SD card which captures actual usage data. The hours per day usage data for each day between visits will be extracted with software provided by the device manufacturer into a format that will be transferred/transcribed to the clinical database.

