Based upon preliminary results from the ongoing Phase 1 clinical study AVXS-101-CL-101, at least 80% of treated symptomatic patients with biallelic- *SMN1* deletions and 2 copies of *SMN2* without the *SMN2* gene modifier mutation (c.859G>C) are expected to achieve the co-primary efficacy endpoint of survival through 14 months of age. It is anticipated that 75% of patients in the PNCR population would not survive beyond 13.6 months of age, and that these control patients will represent a 25% survival rate based upon the natural history of the disease. With this efficacy, an enrolled sample size of 15 patients that meet ITT criteria (assuming 30% of patients are excluded from the analysis) would yield an ITT population that would provide power of > 80% to detect a significant difference from the historical control with  $\alpha = 0.05$  using a 2-sided Fisher's Exact test, comparing to the 26 age and gender matched patients from a published natural history observational study performed at 3 large, tertiary care centers in the United States (Harvard University, Columbia University, Children's Hospital of Philadelphia; PNCR).

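### The survival co-primary would gain about 2 to 6 points of power, on the same 14-month outcome, if Boschloo's unconditional exact test replaced Fisher's exact test

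*Protocol*

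**What the plan says.** The second co-primary endpoint is survival at 14 months of age, meaning freedom from death and from permanent ventilation. In Section 14.3.2 the parameter tested "is the proportion surviving at 14 months of age", compared with the same proportion in natural-history controls. Sitting is tested first; only if that succeeds "will the co-primary endpoint survival improvement be tested using 2-sided Fisher's Exact test on the ITT population".

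Section 14.2 powers this same test at a 2-sided alpha of 0.05. Its inputs are:

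- Treated survival: "at least 80% of treated symptomatic patients with biallelic- *SMN1* deletions" (with 2 *SMN2* copies and no modifier mutation) are expected to survive to 14 months.
- Control survival: "these control patients will represent a 25% survival rate based upon the natural history of the disease", with 26 matched patients.
- Size: "an enrolled sample size of 15 patients that meet ITT criteria (assuming 30% of patients are excluded from the analysis").

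From these, the plan "would yield an ITT population that would provide power of > 80% to detect a significant difference from the historical control". The synopsis describes the controls as "age and gender-matched control patients selected from existing natural history data sets". Endpoint, hypothesis, test and power statement agree with one another.

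**The concern.** Fisher's test conditions on both margins of the 2×2 table. With about ten treated patients and 26 controls, few tables are possible for any given total of survivors, so the attainable significance levels are coarse. The test then works well below the 5% it is allowed, and that unused error rate is lost power.

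This matters here for two reasons. On the plan's own exclusion allowance, power at 10 analysed patients is only just above 80%. And a trial of about 15 infants with a rare disease cannot readily recruit more. If true survival were somewhat below 80%, a real survival benefit could miss significance on a co-primary endpoint because of the choice of test alone.

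**Working it through.** **Inputs (Section 14.2).** Treated survival πT = 0.80; control survival πC = 0.25; control size 26; 2-sided alpha 0.05. Treated size: 15 × (1 − 0.30) = 10.5, so 10 or 11 analysed. The case of all 15 analysed is carried as well.

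**Formula.** With x survivors among n treated and y among 26 controls, and p(x, y) the 2-sided Fisher p-value:

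Power = Σx Σy C(n, x) πT^x (1 − πT)^(n−x) × C(26, y) πC^y (1 − πC)^(26−y) × 1{p(x, y) ≤ c}

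True size is the same sum with πT = πC = π, maximised over π (999-point grid). Fisher's test uses c = 0.05. Boschloo's test takes the Fisher p-value as its statistic and uses the largest c for which the maximum true size stays at or below 0.05. Both are full enumerations with no approximation beyond the grid.

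**Step 1: the plan's own figure.** Fisher's test gives 81.9% (n = 10), 85.9% (n = 11) and 92.6% (n = 15). The stated figure of above 80% is met in each case.

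**Step 2: Fisher against Boschloo at 80% versus 25%.**

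| n treated | Fisher max size | Fisher power | Boschloo max size | Boschloo power | Gain (points) |
|---|---|---|---|---|---|
| 10 | 2.7% | 81.9% | 4.5% | 87.8% | 5.9 |
| 11 | 3.0% | 85.9% | 4.8% | 90.4% | 4.5 |
| 15 | 3.2% | 92.6% | 4.3% | 94.6% | about 2 |

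**Step 3: is anything given up?** The Boschloo cut-offs on the Fisher p-value come out at 0.0599, 0.0700 and 0.0525 for n = 10, 11 and 15. All exceed 0.05, so every table that Fisher's test rejects is also rejected by Boschloo's.

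One table shows the difference: 6 of 10 treated and 6 of 26 controls surviving. There are 12 survivors among 36, and C(36, 10) = 254,186,856.

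- Upper tail (6 or more treated survivors): (9,818,424 + 1,603,008 + 136,620 + 5,280 + 66) / 254,186,856 = 0.0455.
- The opposite tail adds the table with no treated survivors: 1,961,256 / 254,186,856 = 0.0077.
- Fisher p = 0.0455 + 0.0077 = 0.0532.

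Fisher's test does not reject this table. Boschloo's does, because 0.0532 is below 0.0599.

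**Step 4: sensitivity to the treated survival rate (controls 25%).**

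| True treated survival | Fisher, n = 10 / 11 | Boschloo, n = 10 / 11 | Gain (points) |
|---|---|---|---|
| 70% | 62.0% / 66.2% | 70.4% / 74.3% | 8.4 / 8.1 |
| 75% | 72.5% / 76.8% | 80.0% / 83.3% | 7.5 / 6.5 |
| 80% | 81.9% / 85.9% | 87.8% / 90.4% | 5.9 / 4.5 |
| 90% | 95.3% / 97.3% | 97.5% / 98.3% | 2.1 / 1.0 |

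**The case against.** The strongest reply is that nothing here is wrong. Fisher's test is valid, pre-specified and consistent with the hypothesis, and it delivers the stated power. Against external, non-randomised controls, some statisticians would accept or even prefer a conservative test. That stands, and it is why this is an improvement and not a fault. It does not argue against Boschloo's test, which is also exact and holds its size at or below 4.8%. A conservatism that arises only from the coarseness of the table is also not designed to protect against bias from the controls.

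The reply also notes that the gain may be small. The ITT definition in Section 14.1.2.1 covers every qualifying infused patient, so all 15 may be analysed, and the gain is then about 2 points. The 80% is a floor, and Section 5.4 reports no deaths or permanent ventilation in the 12 patients of Phase 1 Cohort 2; at 90% survival the gain is 2.1 points at n = 10 and 1.0 at n = 11. Both points stand. The 30% exclusion, however, is the plan's own planning assumption.

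A reader might infer something stronger: that the power is lost by reducing dated events to a yes/no at 14 months, and that a log-rank test should be primary. The documents do not support this, for four reasons.

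- **Size.** Under proportional hazards with everyone at risk from time zero, a permutation log-rank test gave 88.7%, 90.7% and 95.4%, which is only 0.9, 0.3 and 0.8 points beyond Boschloo's test. A second simulation gave 89.4% and 90.8% at n = 10 and 11, which is 1.6 and 0.4 points beyond. Nearly all of the loss is Fisher's conservatism.
- **Assumptions.** The gain depends on hazard shapes that the protocol does not give. With strongly late-clustered control events (assumed Weibull shape 3), the asymptotic log-rank fell below Fisher's test: 78.7% against 81.6%, and 82.0% against 86.1%. Treated infants also enter at up to 180 days of age. With delayed entry on the age scale (assumed uniform over 0.5 to 6 months), log-rank power was 66% to 75% at n = 10 and 70% to 79% at n = 11. That comparison is not like for like, because Fisher's test ignores the survival that treated infants needed to reach dosing.
- **Data.** Section 12.1.7 says of trial patients that "The hours per day usage data for each day between visits will be extracted". No passage says that individual event dates are held for the 26 controls.
- **Hypothesis.** A log-rank test would replace the stated hypothesis about a proportion at 14 months.

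Nor can the absence of a supportive time-to-event analysis be inferred: the SAP is not shown and part of the endpoint section is redacted.

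**Conclusion.** The point holds as a low-cost improvement. At 80% versus 25% with 26 controls, moving from Fisher's to Boschloo's test gains about 6 points at 10 treated, 4.5 at 11 and 2 at 15. At 70% survival the gain at 10 or 11 treated is about 8 points. At 75% survival, Fisher's power is below 80% at both 10 and 11 patients, while Boschloo's is about 80% and 83%.

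The result rests on the plan's stated rates and control number, and on treating the two groups as independent binomial samples. It needs no event dates, hazard shape or risk-set rule. It does not show that the stated power is wrong, and it does not show that dichotomising at 14 months is what costs the power.

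**What to change.** In Sections 14.2 and 14.3.2, and in the synopsis where the test is named, replace the 2-sided Fisher's exact test with Boschloo's 2-sided unconditional exact test at alpha 0.05. Keep the 14-month endpoint, the hypothesis and the rule that survival is tested only after sitting succeeds. Restate the power for the new test (87.8% at 10 analysed, 90.4% at 11, 94.6% at 15) and report Fisher's p-value as supportive.

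A time-to-event comparison should be at most supportive, and only if event dates exist for the controls and delayed entry is handled explicitly.

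The cost is a wording change and a standard software routine, with no new patients or data. The drawbacks are a less familiar test and a gain of only about 2 points if all 15 ITT patients are analysed.

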Humans also carry a second nearly identical copy of the *SMN1* gene called *SMN2* [11]. Both the *SMN1* and *SMN2* genes express SMN protein; however, the amount of functional full-length protein produced by *SMN2* is only 10 to 15% of that produced by *SMN1* [11,12,13]. Although *SMN2* cannot completely compensate for the loss of the *SMN1* gene, patients with milder forms of SMA generally have higher *SMN2* copy numbers [14,15]. Quantitative analysis of *SMN2* copies in 375 patients with Type 1, 2, or 3 SMA showed a significant correlation between *SMN2* copy number and SMA Type, as well as, duration of survival. In a large early study by Feldkotter et al 2002, 2 copies of *SMN2* was 97% predictive for developing SMA Type 1, 3 copies of *SMN2* was 83% predictive for developing SMA Type 2, and 4 copies of *SMN2* was 84% predictive of SMA Type 3 [16]. As these percentages do not reflect the possible impact of modifier mutations such as that described by Prior et al 2009 [17], they may understate the relationship between copy number (in the absence of a genetic modifier) and clinical phenotype. Among 113 patients with Type 1 SMA, 9 with one *SMN2* copy lived < 11 months, 88/94 with 2 *SMN2* copies lived < 21 months, and 8/10 with 3 *SMN2* copies lived 33 to 66 months. Even more refined data describing this relationship has been generated and has also influenced our choice of the study target group.

The severity of SMA Type 1 is demonstrated by prognosis as illustrated in Kaplan-Meier survival curves shown in Figure 1.

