### 8.2. Patient Exclusion Criteria

Patients must not meet any of the following exclusion criteria:

1. Previous, planned or expected scoliosis repair surgery/procedure during the study assessment period
2. Pulse oximetry < 96% saturation at screening while the patient is awake or asleep without any supplemental oxygen or respiratory support, or for altitudes > 1000 m, oxygen saturation < 92% awake or asleep without any supplemental oxygen or respiratory support  
Pulse oximetry saturation may decrease to < 96% after screening provided that the saturation does not decrease by  $\geq 4$  percentage points
3. Tracheostomy or current use or requirement of non-invasive ventilatory support averaging  $\geq 6$  hours/day over the 7 days prior to the screening visit; or  $\geq 6$  hours/day on average during the screening period or requiring ventilatory support while awake over the 7 days prior to screening or at any point during the screening period prior to dosing

4. Patients with signs of aspiration/inability to tolerate non-thickened liquids based on a formal swallowing test performed as part of screening. Patients with a gastrostomy tube who pass the swallowing test will be allowed to enroll in the study
5. Patients whose weight-for-age is below the third percentile based on World Health Organization (WHO) Child Growth Standards [25]
6. Active viral infection (includes human immunodeficiency virus [HIV] or positive serology for hepatitis B or C, or Zika virus)
7. Serious non-respiratory tract illness requiring systemic treatment and/or hospitalization within 2 weeks prior to screening
8. Upper or lower respiratory infection requiring medical attention, medical intervention, or increase in supportive care of any manner within 4 weeks prior to screening
9. Severe non-pulmonary/respiratory tract infection (e.g., pyelonephritis or meningitis) within 4 weeks before administration of gene replacement therapy or concomitant illness that, in the opinion of the Principal Investigator, creates unnecessary risks for gene replacement therapy such as:
  - a. Major renal or hepatic impairment
  - b. Known seizure disorder
  - c. Diabetes mellitus
  - d. Idiopathic hypocalcuria
  - e. Symptomatic cardiomyopathy
10. Known allergy or hypersensitivity to prednisolone or other glucocorticosteroids or their excipients

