Based upon the widely cited natural history of the disease (Pediatric Neuromuscular Clinical Research Network [PNCr]) [*Neurol.* 2014; 83(9):810-817], it is expected that no patients in this population would be expected to attain the ability to sit without support or accomplish other milestones (rolling over, standing, walking) prior to 18 months of age. Assuming that the true response rate for the primary endpoint is actually zero (or as low as 0.1%) in the population of interest of the historical control, the first co-primary efficacy endpoint hypothesis:

$$\begin{aligned} H_0: p_{AVXS-101} &= 0.1\% \\ &\textit{versus the alternative} \\ H_a: p_{AVXS-101} &> 0.1\%, \end{aligned}$$

where  $p$  is the proportion of functional independent sitting for at least 30 seconds at the 18 months of age study visit.

Based upon preliminary results from the ongoing Phase 1 clinical study AVXS-101-CL-101, at least 40% of treated symptomatic patients with bi-allelic deletions of *SMN1* and 2 copies of *SMN2* without the *SMN2* gene modifier mutation (c.859G>C) are expected to achieve the co-primary efficacy endpoint of functional independent sitting for at least 30 seconds at the 18 months of age study visit. With the assumption for the true response rate of AVXS-101 for

the primary endpoint being in the range of 30% - 40%, a sample size of 15 patients that meet ITT criteria will be enrolled and assuming approximately 30% of patients are excluded from analysis, would yield an ITT population that would provide power of > 90% to detect a significant difference from 0.1% with  $\alpha = 0.025$  using a 1-sided exact test for a binomial proportion.

The second co-primary efficacy endpoint hypothesis:

$$H_0: p_{AVXS-101} = p_{HISTORICAL-FINKEL}$$

*versus the alternative*

$$H_a: p_{AVXS-101} \neq p_{HISTORICAL-FINKEL}$$

where  $p$  is the proportion of patients surviving at 14 months of age.

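### Ability to thrive and ventilatory independence are tested against a 0.1% null that the protocol supports only for motor milestones, so one success would count as superiority to natural history

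*Protocol*

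**What the plan says.** Section 14.3.2 opens by stating the purpose of the primary and secondary analyses: "These analyses are to test the superiority of AVXS-101 to the results from natural observation study (PNCR").

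For the two co-secondary endpoints it writes "The hypothesis for both co-secondary efficacy endpoints to be tested is" and gives a null of 0.1% against a one-sided alternative of more than 0.1%, where p "is the proportion of patients maintaining the ability to thrive/are independent of ventilatory support". The method follows: "One-sided exact binomial tests will be executed for secondary efficacy analyses on the ITT population". No significance level is given for these tests. The testing hierarchy described in the same section covers only the two co-primary endpoints.

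The argument for 0.1% is in the Synopsis (Statistical Methods) and Section 14.2. It is that untreated patients of this genotype are not expected to sit or reach other motor milestones by 18 months of age. It does not mention feeding, weight or ventilation.

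**The concern.** A null of almost zero can be defended for an ability that Type 1 patients, by the protocol's own definition, never acquire. The co-secondary endpoints are different in kind. They ask whether a child still swallows thin liquids, keeps weight and feeds without support, or still needs no daily ventilation, at 18 months. Some untreated children may still do so, and no rate for this is given in the visible text.

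Two things in the protocol point away from 0.1%:

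- **Survival.** Section 14.2 expects that "these control patients will represent a 25% survival rate based upon the natural history of the disease", meaning free of death or permanent ventilation at 13.6 months. Section 5.2 reports that 88 of 94 two-copy Type 1 patients lived less than 21 months, so 6 lived longer.
- **Entry selection.** Section 8.2 excludes infants who fail the swallowing test and "Patients whose weight-for-age is below the third percentile based on World Health Organization (WHO) Child Growth Standards". It also excludes those on 6 or more hours of ventilatory support a day, or needing it while awake.

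If the true untreated rate is above 0.1% by even a small absolute amount, the test does not control error against natural history. A nutrition or ventilation claim described as superiority to PNCR could then rest on one child.

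**Working it through.** **Inputs.** Null rate 0.1% and one-sided exact binomial test (Section 14.3.2). 15 enrolled ITT patients with about 30% excluded, 15 × 0.7 = 10.5, so 10 or 11 analysed (Section 14.2). One-sided level 0.025, stated in Section 14.2 for sitting and assumed here to carry over.

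**The plan's own figure.** The stated power of more than 90% for sitting, at a true rate of 30% to 40%, uses the same null. With a critical value of one success, power is 1 − (1 − p)^n:

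- n = 10: 97.2% at 30%, 99.4% at 40%
- n = 11: 98.0% and 99.6%
- n = 15: 99.5% and 99.95%

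The stated figure is reproduced, so the one-success rule is what the plan implies.

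**Critical value for the co-secondaries.** P(at least 1 success | 0.1%) = 1 − 0.999^n:

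- n = 10: 0.0100
- n = 11: 0.0109
- n = 15: 0.0149

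All are below 0.025, so one success rejects. The same holds at 0.05. At 0.01, one success in 15 would not reject.

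**What one success in 15 shows.** The estimate is 6.7%, exact 95% confidence interval 0.17% to 31.9%. That interval still contains 25%.

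**Largest untreated rate at which error stays within 2.5%.** Solve 1 − (1 − p)^n = 0.025, so p = 1 − 0.975^(1/n). This gives 0.17% at n = 15, 0.23% at n = 11 and 0.25% at n = 10.

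**Probability of declaring an ineffective treatment superior**, 1 − (1 − p)^n. The untreated rates are assumptions, because the documents give none for these endpoints:

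| Assumed untreated rate | n = 10 | n = 11 | n = 15 |
|---|---|---|---|
| 1% | 10% | 10% | 14% |
| 5% | 40% | 43% | 54% |
| 10% | 65% | 69% | 79% |
| 25% | 94% | 96% | 99% |

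**How plausible 0.1% is.** For 0.1% to hold, at most 0.001/0.25 = 0.4% of those event-free at 13.6 months could meet the endpoint at 18 months. Set against 6/94 = 6.4% alive at 21 months, the share is 0.001/0.064 = 1.6%. The second comparison is approximate, because it is read at 21 months rather than 18.

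**The case against.** A reader might infer that the protocol's natural-history figures contradict the 0.1% null. They do not. The 25% is freedom from death, tracheostomy or at least 16 hours a day of ventilation for 14 consecutive days, at 13.6 months. The co-secondary endpoint is no daily ventilator use at 18 months, which is stricter and later. The 6/94 is survival alone. These figures limit the share who could meet the endpoints without measuring it, and every survivor could in principle need some ventilation or tube feeding. This part of the objection stands: 0.1% is unsupported and implausible, not refuted.

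A reader might also infer that most infants already meet both endpoints at entry. The documents give no baseline distribution. Section 8.2 admits gastrostomy patients who pass the swallowing test and infants with less than 6 hours a day of support. Neither group need meet the endpoints.

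A third temptation is to extend the point to sitting, since two *SMN2* copies "was 97% predictive for developing SMA Type 1" (Section 5.2). That fails. The same section says these percentages ignore modifier mutations and may understate the link between copy number and phenotype. The ITT population excludes the modifier and requires symptomatic patients treated before 180 days, whereas Table 4 places Type 2 onset at 6 to 18 months. The remaining 3% is therefore not a background sitting rate.

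Two limits remain. Section 14.1.1.2, on the co-secondary endpoints, is not visible, and the SAP was not available. However, the null and the test are fixed in Section 14.3.2, so this is not a detail left for later. And a high observed proportion would still be informative; the defect is in the significance test and the claim attached to it.

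**Conclusion.** The point holds for the two co-secondary endpoints. The 0.1% null is carried over from motor milestones without a visible basis for thriving or ventilatory independence, and a test against it cannot show superiority to PNCR.

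The size of the problem depends on the unknown untreated rate. At the planned 10 or 11 analysed patients, false-positive probability runs from about 10% at an untreated rate of 1% to 94–96% at 25%. With all 15 analysed it runs from 14% to 99%. The upper end uses a survival ceiling and should not be read as an estimate, but 1% is already well above the nominal level.

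The figures rest on the 0.025 one-sided level carrying over. The co-primary tests and their hierarchy are not affected.

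**What to change.** In Section 14.3.2, remove the 0.1% null for both co-secondary endpoints and state the significance level. Then choose one of these:

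1. Set each null from PNCR data on that endpoint in comparable patients, for example the upper confidence limit of the PNCR rate.
2. Compare with the PNCR controls by Fisher's exact test, placed after survival in the hierarchy.
3. If PNCR does not hold these data, which the documents do not settle, report each proportion with an exact confidence interval and drop the superiority claim. For ventilatory independence only, the 25% event-free figure could instead serve as a null, labelled as a deliberately conservative ceiling.

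The cost is protocol and SAP wording, plus a higher bar and lower power. With a 25% null at one-sided 0.025:

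| Analysed | Successes needed | Attained level | Power at a true 70% |
|---|---|---|---|
| 15 | 8 | 0.017 | 95% |
| 11 | 7 | 0.008 | 79% |
| 10 | 6 | 0.020 | 85% |

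A lower PNCR-based null would ask for less: at 5% or 10%, 4 or 5 successes of 15. No change to the sitting or survival tests is proposed.
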